6.2 Secondary Objectives

The secondary objectives are:

1. Central collection of clinical data on CAP
2. Improvement of prevention through evaluation of vaccination behavior
3. Timely identification of high-risk patients
4. Reduction of CAP morbidity (through improved CAP management and therapy of comorbid diseases)
5. Definition of risk factors for unusual pathogens or a severe course of CAP in patients with immunosuppression

6.3 Background

Community acquired pneumonia is a widespread and frequent disease. Approx. 350,000 patients with CAP are admitted to hospital every year (Struß R et al., Dtsch Arztebl Int. 2014 Jul 21; 111(29-30):503-8). Meaning that community acquired pneumonia patients are admitted to hospital more often than the more commonly known widespread diseases of heart attack (132,000 admissions) and stroke (162,000 admissions). The costs for the disease amount to more than 500 million Euro every year. Overall mortality still is 6-8 %. Community acquired pneumonia is therefore the sixth most often cause of death in Germany at present.

In spite of the importance of community acquired pneumonia there is still a huge lack of reliable data on the pathogen spectrum, the resistance profile of the pathogens and on the course of the disease. The

Federal Ministry of Education and Research recognized these deficits and initiated the excellence network for community acquired pneumonia, in short CAPNETZ, in the year 2001.

Since that time, CAPNETZ has networked various groups and organizations from all areas of medicine that are focusing on this disease in order to collect pneumonia-specific data.

Up to the end of 2018, approx. 13,000 patients with community acquired pneumonia have been included. All clinical and microbiological data have been collected and a central biomaterial as well as information database has been established. Among others, the following questions have been investigated and will be investigated:

1. How often do which pathogens cause community acquired pneumonia?
2. What is the resistance situation of pathogens in Germany?
3. Are there certain markers in blood, allowing a forecast about the severity of pneumonia?
4. Do existing official recommendations concerning the diagnosis and therapy of community acquired pneumonia have to be revised?
5. How can a better acceptance of vaccinations be achieved?
6. What causes bacteria to become invasive? Why can the endogenous immune system not prevent the disease?

Approximately 20% of all patients with CAP have underlying congenital, acquired or therapy-associated immunosuppression (di Pasquale et al., Clin Infect Dis 2019). There are still very few data about importance, risk factors, pathogen spectrum and course of CAP for this important patient group. Consequently, they are excluded from all national and international guideline recommendations for the management of CAP. Therefore, patients with immunosuppression are also to be evaluated within the established CAPNETZ study cohort in order to establish a database for future management recommendations.

The results of the CAPNETZ study are not only made available to their participants.

Researchers and research groups can apply for the use of clinical data and biomaterials for their current questions in CAP research and the research of other acute respiratory infections. In the past, through its research, the CAPNETZ FOUNDATION has set the basis for a widening understanding of pneumonia and has supported better and more comprehensive care of patients. Results of the CAPNETZ study impact the S3-guidelines for community acquired pneumonia.

6.4 Project Structure and Legal Aspects (Sponsors)

The CAPNETZ FOUNDATION was founded in 2008 as a foundation for civil rights and fulfills solely and directly charitable purposes.

1. The foundation is listed in the foundation register of the state of Baden-Württemberg. The foundation headquarters is Ulm.
2. The financial year is the calendar year.

All details of the CAPNETZ FOUNDATION are regulated in the Statute of the Foundation.

6.4.1 Purpose, Tasks and Objectives of CAPNETZ

The purpose, tasks and objectives of CAPNETZ are:

1. Since 2008 the CAPNETZ FOUNDATION is responsible for the network and serves the establishment and continuation of the CAPNETZ network beyond the funding period of the BMBF from 2001-2011.
2. The purpose of the foundation is the support of science and research in the field of community acquired pneumonia and other acute diseases of the lower respiratory tract. This includes studies in the fields of basic research, microbiological research, and all forms of clinical studies (prevention, vaccination, diagnostic and therapeutic studies). Additionally, the foundation is to contribute towards improving the collaboration between leading research institutions in Germany (horizontal networking), speeding up the knowledge transfer from research to practice (vertical networking) and promoting the education of the general public about this disease. A key objective of the foundation is to significantly reduce morbidity and mortality of this disease through education, prevention and better understanding, thus also reducing the economic burden on the health system.

The CAPNETZ FOUNDATION shall continue its successful work of the past years and work on clinically relevant questions concerning the topic of inflammatory lung diseases. The foundation makes a relevant contribution to safeguarding the future for pneumonia research and it promotes synergies between different institutions and organizations. Current funds are raised from EU, federal, public and private funding, as well as from industry-funded clinical studies. Donations are also used for research purposes by the foundation.

6.4.2 Scientific Projects based on CAPNETZ Data and Biomaterials

Researchers who wish to carry out projects within the framework of the Foundation's objectives can apply for the use of clinical data from the CAPNETZ database as well as for biomaterials. This can be done using the CAPNETZ online portal.

To apply, a project outline must be submitted; the appropriate form is available online. Every submitted application which is approved by the executive board of the Foundation is supervised by a designated member of the board in order to support a successful completion. A timetable including milestones will be agreed with each applicant and retained in the project outline. If the applicant for important reasons cannot keep to the timetable, the board will be informed in writing immediately via the e-mail address [contact]. The timetable can then be adjusted accordingly by the board. When considerable delays occur, projects can be stopped and additional work is no longer possible.

The CAPNETZ Office is responsible for the documentation and timely organization of the submitted research projects. On request, it provides assistance with the submission of projects.

When implementing scientific projects, the Publication Strategy of the CAPNETZ FOUNDATION is to be met. This strategy is available to the applicant.

6.4.3 CAPNETZ Office

The tasks of the CAPNETZ Office are:

1. The CAPNETZ Office is the central interface for internal and external data exchange and responsible for all network activities: planning, design and implementation in close communication with CAPNETZ participants. On the other hand, it is also responsible for ensuring a smooth flow of information within the network and serves as a contact and forwarder for questions, suggestions, or comments from the network and the general public to appropriate CAPNETZ members. The CAPNETZ Office is also responsible for the central CAPNETZ database in cooperation with the IT company 2mt Software Ltd. The CAPNETZ Office determines deadlines and forms for the archiving and deletion of stored data in accordance with the legal regulations.
2. The CAPNETZ Office is the formal and technical quality assurance entity in the network and responsible for data safety issues.
3. The CAPNETZ Office supports the board and the foundation's council in their tasks of coordination, implementation and quality assurance. Apart from the researchers and research groups, the CAPNETZ Office is also responsible for the compliance with the legal data protection regulations.
4. The CAPNETZ Office is responsible for the orderly financial management of CAPNETZ.

6.5 Members of the Network

6.5.1 Local Clinical Centers (LCCs)

The local Clinical Centers (LCCs) represent different geographical regions within Germany and other European countries. They are led by proven experts in the field of respiratory medicine. The LCC leads are named by CAPNETZ to coordinate local participating registered physicians, radiologists and microbiological laboratories.

Potential patients in the CAPNETZ study could be registered as an inpatient, as well as an outpatient of a clinical center or as an outpatient in practicing networks. Radiological diagnostics is performed in the framework of clinic routine with practicing radiologists or in the radiological department of the clinic. Radiological evidence of a pulmonary infiltrate is primarily found by conventional chest x-ray or via computed tomography of the thorax. The LCC's microbiological laboratories are responsible for processing of the patient samples, for routine diagnostics, for the preservation and dispatch of gained biomaterials to the CAPNETZ biobank. This is situated at the Hannover Medical School (Hannover Unified Biobank, HUB). A current overview of the LCCs network can be found at <http://www.capnetz.de/html/patients/locations>.

6.5.2 Central CAPNETZ Biobank

The services of the Central CAPNETZ biobank at the Hannover Medical School can be summarized as follows:

CAPNETZ STIFTUNG Geschäftsstelle • Medizinische Hochschule Hannover
[name] • [contact] • [contact]
[contact] • www.capnetz.de

Administration, quality management, sample shipping, processing and storage for scientific purposes of the CAPNETZ FOUNDATION.

Address:

Hannover Unified Biobank (HUB)
Medizinische Hochschule Hannover
CRC Hannover
[name]
[name]

The Management system of the biobank is certified by TÜV NORD according to DIN EN ISO 9001:2008.

7 Study Design

Currently there are approx. 13,000 patients in the prospective-observational study, the CAPNETZ study. The patients are individually followed-up (successively from the reference date 01.07.2002) for a time period of six months. The patients are identified in the outpatient or inpatient departments of the hospitals or practices and are recruited by their treating physicians (mainly specialists). All of the patients who fulfill the inclusion and exclusion criteria and who are verified as having newly acquired non-nosocomial pneumonia are invited to participate. No interventions are planned for this study; the physicians treat their patients as they usually do.

8 Patients

8.1 Sample size

It is planned that within the study duration from 01.01. 2020 approx. 500 patients will be included each year in order to obtain representative data for prevalence and incidence estimation.

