Study aim:	Examination of prevalence, incidence and risk factors of community acquired pneumonia (CAP) and its interaction with comorbid diseases in a representative sample of outpatients and inpatients
Patients:	Male and female patients ≥ 18 years of age
Study design:	Prospective and observational study
Main objectives:	
• Estimation of prevalence/incidence of CAP• Examination of the reciprocal relation between CAP and comorbidity• Evaluation of CAP in immunosuppressed patients• Determinants of CAP in HIV patients• Establishment of a database on antimicrobial resistance• Information concerning pathogens and pathogen/host interaction• Establishment of a genetic database concerning pathogens and strains of CAP patients
Study arms:	
1) Outpatients or inpatients with CAP, without HIV infection2) Outpatients or inpatients with CAP, with HIV infection3) Outpatients or inpatients with CAP, with Immunosuppression
Interventions:	None prescribed or planned
Inclusion criteria:	
• Age ≥ 18• Radiological proof of pulmonary infiltrate (primarily chest x-ray or CT)• Signed informed consent
Further inclusion criteria (at least one should be fulfilled):	
• Presence of cough• Presence of purulent sputum• Pathologic lung auscultation (crackles)• Fever
Exclusion criteria:	
• Hospitalization longer than 48 hours prior to diagnosis of current pneumonia• Non-infectious infiltrate• Newly diagnosed, active pulmonary tuberculosis within the last 2 months
Study duration:	Unlimited, depending on funding possibilities (study duration according to funding duration)
Examination time points:	Inpatients only: Visit 1/baseline, visit 2 after 3-5 days, visit 3 after 7-10 days, telephone interviews after 4 weeks and after 6 months from inclusion date

Outpatients only:

Visit 1/baseline, telephone interviews after 4 weeks and after 6 months from inclusion date

Examinations:

Inpatients only:

- Baseline: anamnesis (incl. pneumonia-specific medication and co-mediation of chronic underlying diseases and comorbidities), physical examination, laboratory tests, chest x-ray, hospitalization within the last 3 months, for HIV patients with community acquired pneumonia an additional data entry form, for immunosuppressed patients an additional data entry form

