6.1 Primary Objectives

The main objectives are:

1. Estimation of prevalence/incidence of CAP
2. Improvement of diagnostic accuracy through integration of clinical and microbiological data
3. Documentation of comorbid diseases and analysis of their role as a risk factor
4. Investigation of the influence of CAP on the course of chronic underlying diseases
5. Investigation of HIV as a risk factor
6. Evaluation of importance, risk factors, spectrum of pathogens and course of community acquired pneumonia in patients with pre-existing congenital, acquired or therapy-associated immunosuppression
7. Establishment of a central sample and strain biobank
8. Establishment of a central database concerning antimicrobial resistance
9. Information about pathogens and pathogen/host interaction
10. Establishment of a genetic database concerning pathogens and strains

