8.2 Inclusion Criteria

The following inclusion criteria must be fulfilled:

- Age ≥ 18
- Radiological proof of pulmonary infiltrate (primarily by chest x-ray or CT)
- Signed informed consent

Further inclusion criteria (at least one must be fulfilled):

- Presence of cough
- Presence of purulent sputum
- Pathological lung auscultation (crackles)

- Temperature $\geq 38,3^{\circ}\text{C}$ (rectal) or $\geq 37,8^{\circ}\text{C}$ (axillary/oral/auricular/sublingual)

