8.3 Exclusion Criteria

None of the following criteria may be fulfilled:

- Hospitalization longer than 48 hours prior to diagnosis of current pneumonia
- Non-infectious infiltrate
- Newly diagnosed, active pulmonary tuberculosis within the last 2 months

9 Patient Recruitment

The patients are included in the LCCs either as out- or inpatients.

The study begins with patient recruitment, whereby the inclusion and exclusion criteria of potential patients are tested. The maximum timeframe between presentation with CAP and inclusion as CAPNETZ patient is 48 hours. The study doctor informs a potential CAPNETZ patient about the CAPNETZ study and asks to sign the written informed consent. This includes a general declaration of consent to take part in the CAPNETZ study, as well as further consent for the use of blood samples for genetic examination (GENCAP).

After the patient's consent, he/she will be registered as a case in the CAPNETZ study. Using the identification data of the patient, the study doctor or a member of the study team will create a patient pseudonym using the CAPNETZ study online portal. The originals of the declaration of patient consent remain with the physician. The patient receives copies of the consent declarations.

Electronic data collection is performed by the study doctor and/or by the study personnel. After finalizing the data collection (recording the survival status after 6 months) and after ensuring the accuracy of the collected data the study documentation will be kept in the local clinical center for at least 10 years.

10 Study Implementation

The patients who fulfill the selection criteria and whose consent declaration has been handed in following previous information and advice now undergo a start-up examination (baseline) including medical history (Para. 13.1), medication anamnesis (Para. 13.2) and a short physical examination (Para. 13.4).

The obtained information and examination results as well as particulars about current therapy are documented.

Examinations for hospitalized patients:

Baseline:

During this visit, a patient anamnesis and the demographic data are recorded.

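### CAP prevalence and incidence are primary objective 1 and the only stated reason for the sample size, but the cohort as described enrols only consenting CAP cases and has no population denominator

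*Protocol*

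**What the plan says.** **The objective.** The synopsis gives the prevalence and incidence of CAP as part of the study aim and puts their estimation first among the main objectives. Section 5 and the opening of Section 6 repeat this, and item 1 of Section 6.1 reads "Estimation of prevalence/incidence of CAP".

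**The sample size.** Section 8.1 states that "approx. 500 patients will be included each year in order to obtain representative data for prevalence and incidence estimation". No other reason is given for the number.

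**Who is enrolled.** Under Section 7, all patients who meet the selection criteria and "who are verified as having newly acquired non-nosocomial pneumonia are invited to participate". The first study arm in the synopsis is "Outpatients or inpatients with CAP, without HIV infection"; the other two arms are CAP with HIV infection and CAP with immunosuppression. Section 8.2 requires a radiologically proven infiltrate and signed consent of everyone. Section 9 adds: "After the patient's consent, he/she will be registered as a case in the CAPNETZ study".

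**Who drops out of the record.** Section 15.3 concerns incapacitated patients. If such a patient dies without consent having been obtained, if consent cannot be obtained later, or if the patient refuses, the samples and all data are destroyed.

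**The source population.** Section 6.5.1 says that the centres "represent different geographical regions within Germany and other European countries". That describes where they are and does not define a population at risk.

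**The concern.** Incidence is new cases divided by person-time at risk. Prevalence is existing cases divided by the persons among whom they were counted. Both need a denominator that includes people without the disease, and a numerator that is complete or has a known capture fraction. A cohort made up only of enrolled cases supplies neither.

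This affects the first primary objective and the whole stated basis for the sample size. A count of enrolled patients presented as a CAP rate would mix disease occurrence with referral, invitation and consent, with no means of separating them. Section 6.3 says that results of the study feed into national guidelines, so a rate read at face value could travel far.

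A statistical analysis plan could not repair this. It can specify an estimator, but it cannot create a denominator or a record of missed cases that the design does not collect.

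**Working it through.** **1. Can the figure of 500 be reproduced?** No. The protocol gives no expected rate, target precision, denominator or capture fraction, so no formula leads to 500 per year.

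**2. What is needed against what is described.**

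| Needed for CAP prevalence or incidence | What the protocol describes |
|---|---|
| Population at risk or person-time | None; about 20 to 30 centres (synopsis), with regions but no population sizes (Section 6.5.1) |
| People without CAP | None; all three arms are CAP patients (synopsis), and an infiltrate is mandatory (Section 8.2) |
| All cases in that population, or a known capture fraction | Consenting cases only (Sections 8.2 and 9), recruited mainly by specialists (Section 7); no log of eligible patients not enrolled is described; some records are destroyed (Section 15.3) |
| Linkage to outside population or case counts | None described |

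The proportion with CAP among participants is 100% by construction and carries no information about prevalence.

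**3. Is this a matter of sample size?** Two sources of uncertainty can be compared.

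- *Sampling error.* For a Poisson count of 500, the relative 95% half-width is 1.96/√500 = 0.088, or about ±8.8%.
- *Missing denominator and capture.* Incidence = 500/(c × N), where N is the catchment population and c is the fraction of all cases enrolled. The protocol gives neither, so both ranges are assumptions: N from 1 to 10 million, c from 1% to 100%.
  - N = 1 million, c = 1%: 500/(0.01 × 1,000,000) = 50 per 1,000 per year.
  - N = 3 million, c = 10%: 500/(0.10 × 3,000,000) = 1.67 per 1,000 per year.
  - N = 10 million, c = 100%: 500/(1.00 × 10,000,000) = 0.05 per 1,000 per year.

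The range is 50/0.05 = 1,000-fold. Its exact width reflects the assumed ranges. What matters is that neither c nor N can be learned from the enrolled patients, so raising the number enrolled shrinks only the ±8.8%.

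**4. What 500 per year can support.** For a proportion p among enrolled patients, the 95% half-width is 1.96 × √(p(1 − p)/500):

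- p = 0.20: 1.96 × √(0.16/500) = 0.035, or 3.5 points.
- p = 0.50: 1.96 × √(0.25/500) = 0.044, or 4.4 points.

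These are for one year's intake and treat patients as independent. With 500 patients over 20 to 30 centres, or about 17 to 25 per centre, clustering would widen them. The protocol gives nothing from which to quantify that.

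**The case against.** **Enrolment may be close to consecutive.** Section 7 says that all eligible patients are invited, and Section 16.1 obliges centres to inform all potential patients. The figure is approximate, and no cap at 500 is set. This stands. A reader might infer that the count is driven by a quota, or by whom centres choose to enrol; the documents do not support that. Consent, incomplete uptake and the destruction of some records still leave the capture fraction unknown, and even complete capture would leave the denominator missing.

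**A log may exist.** The protocol does not list every form or centre record. One can therefore say only that no count of eligible, non-enrolled cases is described, not that none is kept.

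**An external denominator could be added.** With complete case ascertainment and a defined source population, incidence might be estimable. This rules out any claim that the objective could never be met. The protocol plans neither element.

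**Prevalence might mean features among CAP patients.** Section 6.1 names prevalence and incidence of CAP itself and lists comorbidity, immunosuppression, resistance and pathogens as separate objectives, so this reading does not fit the text.

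**The cohort might be read as a sample of patients in general.** The opening of Section 6 speaks of an unselected group of adults in GP, specialist and inpatient care. Such a group could serve as a denominator, but the selection criteria admit only those with CAP.

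**The consequences are limited.** This is a non-interventional, descriptive study; no test or treatment decision hangs on the objective, and the other nine primary objectives do not need a CAP rate. That is fair, and it limits the damage to objective 1 and the sample-size rationale.

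**Conclusion.** The mismatch between objective and design is real. From this cohort as described, neither prevalence nor incidence of CAP can be estimated, and a larger sample would not change that. The conclusion is structural: it follows from the selection criteria and from the absence of any described denominator. It does not depend on the assumed catchment or capture ranges, which only illustrate that the obstacle is not precision.

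A reader might go further and put a size on the bias, for example by dividing 500 by an assumed catchment and comparing the result with the roughly 350,000 yearly CAP admissions in Section 6.3. The documents do not support such a figure. They give no catchments, that count covers inpatients only while the cohort also takes outpatients and centres in other countries, and the protocol nowhere says it will make that division. As an order of magnitude only, 500/350,000 is about 0.14%.

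Nor does the point invalidate the rest of the study. Frequencies of pathogens, resistance, comorbidity and immunosuppression can be estimated among enrolled, consenting patients. Mortality needs more care, because Section 15.3 removes some incapacitated patients who die before consent is obtained.

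**What to change.** - In the synopsis, Section 5, Section 6, item 1 of Section 6.1 and Section 8.1, delete the prevalence and incidence of CAP, or reword it to frequencies among enrolled, consenting CAP patients (for example pathogens, resistance, comorbidity, immunosuppression). Since several of these are already primary objectives, deletion may be enough.
- Restate Section 8.1 as the approximate precision of one year's intake: a 95% half-width of about 3.5 points for a proportion of 20% and 4.4 points for 50%, noting that clustering by centre is not yet allowed for.
- If incidence is kept, say that it requires external case counts and a defined source population, and that enrolment counts will not be used for it.
- Label any mortality estimate as applying to consenting patients, with a reference to Section 15.3. The 6–8% in Section 6.3 is not a suitable basis for a precision statement, because it has no time horizon.

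The rewording costs a protocol amendment and its ethics review and needs no new data. The downside is a less ambitious stated objective. Keeping incidence would cost more, since the source population and the external counts would have to be defined and obtained.
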